8.4.2 Safety analyses

Tabulations and descriptive summaries of adverse events (AEs) and serious adverse events (SAEs) will be reported as described in Section 8. Adverse events will be compared among the comparator groups of the study.

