1. PROTOCOL SUMMARY

1.1 Schedule of Activities (SoA)

1. Participants will be screened for eligibility with medical history, physical exam, prior treatment, history of anemia and blood tests including baseline CBC, reticulocyte count, ferritin, B-12 and serum folate level
2. If inclusion criteria are met and after signing a consent form, participants will start olaparib 300 mg twice daily, commercially approved
3. Assessment of CBC/serum folate will occur every 2 weeks for the first 3 months and then monthly for a total of 6 months from the time of enrollment onto study therapy. If the patient develops folate deficiency and requires folate replacement, CBC/serum folate and reticulocyte count will occur every 2 weeks for 12 months.
4. One-time measurement of serum folate to occur one month after completion or discontinuation of therapy with olaparib
5. If folate deficiency is identified (defined as any level below normal) at any time point, the following parameters will be assessed in 2 weeks or at the next visit/assessment point: a repeat CBC/serum folate level along with B-12, LDH, reticulocyte count, methylmalonic acid, and homocysteine. These labs (CBC/serum folate level, B-12, LDH, reticulocyte count, methylmalonic acid, and homocysteine) need to be drawn once- 2 weeks after initial folate deficiency is identified for confirmation purposes and to rule out co-existing B-12 deficiency or other causes of anemia.
6. Once folate deficiency is confirmed in the setting of hemoglobin (Hgb) less than 12 g/dl but above 10.0 g/dl, patients will be randomized to folate supplementation or placebo. At that point, assessment of CBC/reticulocyte count and folate levels will continue every 2 weeks.
7. If Hgb is above 12.0 g/dl and no folate deficiency is identified, patients will not be randomized. Assessment of CBC/serum folate will continue every 2 weeks for the first 3 months and then monthly for a total of 6 months from the time of enrollment onto the study.
8. If folate deficiency is identified in setting of Hgb less than 10.0 g/dl, patients will not be randomized but will receive folic acid supplementation at 1 mg daily. These patients will have weekly assessments of CBC/reticulocyte count and folate levels until Hgb improves to a level above 10.0 g/dl. At that point, assessment of CBC/reticulocyte count and folate levels will change back to every 2 weeks. However, folic acid replacement will continue as initiated.

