2. OBJECTIVES AND ENDPOINTS

Primary objective:

To determine the frequency and timing of folate deficiency in patients with solid tumors harboring molecular alterations such as germline and somatic mutations in *BRCA1* and *BRCA2* genes, other genes in Homologous DNA Recombination Repair (HRR) pathway, genomic stability as determined by Homologous Recombination Deficiency (HRD) assay, etc., who are treated with olaparib.

Secondary objectives:

To evaluate the effect of folic acid supplementation on serum folate, hemoglobin level, transfusion needs/number of transfusions, and need for olaparib treatment interruption, dose reduction and drug discontinuation.

To assess response rate (RR) to olaparib as it relates to serum folate level and folic acid supplementation.

Clinical Study Protocol - 6
Olaparib - ESR-18-13807

To assess progression-free survival (PFS) as it relates to serum folate level and folic acid supplementation.

Exploratory objectives:

To elucidate the mechanism of folate deficiency in patients treated with olaparib including possible interaction with germline *BRCA1* and *BRCA2* mutations via testing for folate receptors using immunohistochemistry on available paraffin embedded tumor samples from enrolled patients.

Primary endpoint:

The primary binary endpoint of the study is the percentage of patients who develop drug-induced folate deficiency, defined as serum folate level <7 ng/mL, within three months from start of olaparib therapy.

Secondary endpoints:

To assess the impact of folic acid supplementation on anemia, need for transfusion, and olaparib treatment interruption, dose reduction and drug discontinuation as compared to those who did not receive/require folic acid supplementation

To determine tumor response rate (RR), using treating physician assessment, on olaparib therapy in patients who develop folate deficiency and receive folic acid supplementation as compared to those who do not receive/require folic acid supplementation. Will also compare RR to historical controls (patients with solid tumors treated with olaparib or other approved agents on clinical trials).

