3.4 End of study definition

The end of study is defined as 7 months from enrolment. This is to include the one-month follow up physical exam, concomitant medications, adverse effects, and folate level

Clinical Study Protocol - 6
Olaparib - ESR-18-13807

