7.3.2 Time period and frequency for collecting AE and SAE information

Adverse Events will be collected from time of enrolment throughout the treatment period and including the follow-up period until the last contact.

All SAEs will be recorded and reported to the sponsor or designee within 24 hours. The investigator will submit any updated SAE data to the sponsor within 24 hours of it being available.

Investigators are not obligated to actively seek AE or SAE in former study patients. However, if the investigator learns of any SAE, including a death, at any time after a patient's last visit and he/she considers the event to be reasonably related to the Study treatment or study participation, the investigator may notify the sponsor.

Clinical Study Protocol - 6
Olaparib - ESR-18-13807

The method of recording, evaluating, and assessing causality of AE and SAE and the procedures for completing and transmitting SAE reports are provided in CRF.

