7.3.7 Adverse events based on examinations and tests

The results from the Clinical Study Protocol mandated laboratory tests and vital signs will be summarised in the CSR. Deterioration as compared to baseline in protocol-mandated laboratory values, vital signs should therefore only be reported as AEs if they fulfil any of the SAE criteria or are the reason for discontinuation of treatment with the investigational product.

If deterioration in a laboratory value/vital sign is associated with clinical signs and symptoms, the sign or symptom will be reported as an AE and the associated laboratory result/vital sign will be considered as additional information. Wherever possible the reporting Investigator uses the clinical, rather than the laboratory term (e.g., anaemia versus low haemoglobin value). In the absence of clinical signs or symptoms, clinically relevant deteriorations in non-mandated parameters should be reported as AE(s).

Deterioration of a laboratory value, which is unequivocally due to disease progression, should not be reported as an AE/SAE.

Any new or aggravated clinically relevant abnormal medical finding at a physical examination as compared with the baseline assessment will be reported as an AE unless unequivocally related to the disease under study, see Sections 8.3.9 and 8.3.10.

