8.4 Statistical analyses

8.4.1 Efficacy analyses

Patients will be monitored for development of anemia and folate deficiency at scheduled time points throughout the course of the study, as described in Section 1.1. Patients who develop \leq G2 cytopenias and folate deficiency will be randomly assigned in a 1:1 ratio to receive folic acid supplementation 1 mg daily or no supplementation. Patients who develop G3 or higher cytopenias and folate deficiency will be started on folic acid supplementation, thus not included in the randomization. For patients who are randomized, we will assess the impact of folic acid supplementation on anemia, need for transfusion, and dose interruption, dose reduction and drug discontinuation of olaparib as compared to those who did not receive/require folic acid supplementation. Additionally, PFS and RR to olaparib will be compared amongst randomized patients relative to folic acid supplementation.

The statistical analysis will provide descriptive summaries as well as 95% confidence intervals for the primary endpoint of drug-induced folate deficiency in addition to response rate and other secondary endpoints. Kaplan-Meier methodology will be used to estimate the PFS curve and estimate of median PFS and corresponding 95% confidence interval will be provided. The significance of the observed percentage of folate-deficient cases will be assessed by statistical hypothesis test, as well as by multivariable analysis of the binary endpoint of folate deficiency adjusted by important covariates. Covariates will include age, race/ethnic group, previous therapy, Hgb prior to olaparib therapy, genetic testing result (*BRCA* carrier status). RR and PFS will be compared to historical controls as a descriptive comparison. Analyses will be reported on the entire combined cohort of patients with solid tumors and also separately for each cancer type. The statistical analysis of the exploratory endpoint will be specified in the SAP. Statistical analysis will be performed in the R Statistical software. No adjustment for multiplicity will be made.

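### Adverse events are compared across undefined groups with no common cut-off, while the protocol gives both a 12-month schedule and a 7-month end of study

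*Combined protocol and SAP*

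**What the plan says.** Section 8.4.2 plans tabulations and descriptive summaries of adverse events (AEs) and then states: "Adverse events will be compared among the comparator groups of the study". It refers to Section 8 for the method, but Section 8 adds nothing on AE windows, denominators or groups. Section 8.3 puts every patient with at least one olaparib dose into the safety population.

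Three places bear on how long AEs are observed:

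- Section 7.3.2: "Adverse Events will be collected from time of enrolment throughout the treatment period and including the follow-up period until the last contact".
- Section 1.1, item 3: for a patient who becomes deficient and "requires folate replacement, CBC/serum folate and reticulocyte count will occur every 2 weeks for 12 months". Other patients are followed for 6 months in total. Table 1.1.1 B marks AE review in its two-weekly column.
- Section 3.4: "The end of study is defined as 7 months from enrolment", and then "This is to include the one-month follow up physical exam, concomitant medications, adverse effects, and folate level". No exception is made for folate replacement.

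On the groups, the secondary endpoints in Section 2 set folic acid supplementation against a comparator worded "as compared to those who did not receive/require folic acid supplementation", and Section 7.1.1 does the same. Section 8.4.1 is framed around randomisation: "For patients who are randomized, we will assess the impact of folic acid supplementation on anemia, need for transfusion". Deficient patients with Hgb below 10 g/dl receive folic acid without being randomised (Section 1.1, item 8). Randomised patients who fall below that level while deficient receive it whatever their arm (Section 3.1).

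**The concern.** A crude AE count or percentage depends on how long each patient is watched and on when counting starts. Here both can differ systematically between patients who receive folic acid and patients who never need it.

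First, recipients may be followed for 12 months and the others for 7, and longer observation alone yields more events. Second, recipients start folic acid only after deficiency has appeared on olaparib. Some of their observation is therefore unsupplemented. If patients are grouped by whether they ever received folic acid and events are counted from enrolment, events before the first dose are attributed to it.

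Section 8.1 hypothesises that folic acid mitigates the adverse events tied to olaparib's haematological toxicity. An artefact of follow-up could be misread as harm from folic acid, or could hide a benefit.

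**Working it through.** The plan gives no figure for the AE comparison, so there is nothing to reproduce. The check asks what a crude comparison shows when the true monthly AE rate is the same in both groups.

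**Inputs from the protocol**
- Recipients, if item 3 of Section 1.1 governs: 12 months. Item 3 does not say whether this runs from enrolment or from deficiency; I take enrolment.
- Never-required patients: 7 months from enrolment, one-month follow-up included (Section 3.4).
- Recipients, if Section 3.4 governs: 7 months.

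**Assumptions (not in the documents)**
- Constant AE rate, equal in all groups and states: 0.02 to 0.20 per patient-month.
- Folic acid starts at month 1, 2 or 3. For randomised patients, a first scheduled test at week 2 with confirmation two weeks later makes month 1 about the earliest start.
- No loss from observation before the scheduled end.

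**Step 1. The 12-month schedule is followed**
- Ratio of expected event counts = 12/7 = 1.71, whatever the rate.
- Ratio of patients with at least one AE = (1 − exp(−12r)) / (1 − exp(−7r)).
 - r = 0.02: 0.213/0.131 = 1.63.
 - r = 0.20: 0.909/0.753 = 1.21.

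**Step 2. The 7-month end binds for everyone**
- Ratio of counts from enrolment = 7/7 = 1.0.
- Share s/7 of recipients' time that precedes folic acid: 1/7 = 14%, 2/7 = 29%, 3/7 = 43%.
- At a constant rate, the same share of the events credited to folic acid would have occurred before it was started.

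**Step 3. Example with assumed numbers** (25 patients per group, rate 0.04 per month, folic acid from month 2)
- Never-required: 25 × 7 × 0.04 = 7 events in 175 patient-months.
- Recipients to 12 months: 25 × 12 × 0.04 = 12 events in 300 patient-months. The crude comparison is 12 vs 7, yet both rates are 0.04.
- Recipients to 7 months: 25 × 2 × 0.04 = 2 events before folic acid and 25 × 5 × 0.04 = 5 after. The crude comparison is 7 vs 7, but 2 of the recipients' 7 events predate the treatment.

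**Step 4. Randomised arms**
Section 1.1 item 6 and Table 1.1.1 B give two-weekly checks after randomisation without separating the arms. The schedule creates no difference in observation between them.

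**The case against.** The best defence reads Sections 7.3.2 and 3.4 together: AEs are collected from enrolment, and the study, with its adverse-effects follow-up, ends at 7 months. Item 3's 12 months names only laboratory tests, and the AE marks in Table 1.1.1 B carry no duration. On that reading the windows are equal. Section 8.4.2 also leaves its groups undefined. The wording about patients who did not receive or require folic acid belongs to the anaemia, transfusion, olaparib dosing and tumour outcome endpoints, and Section 8.4.1 frames the folic acid analyses around randomised patients. Finally, this is a pilot with descriptive AE tables, and AE dates are collected (Section 7.3.4), so patient-time tables could be produced anyway.

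Much of this stands. The 1.7 depends on the 12-month schedule being followed, and the comparison with never-required patients is inferred. But nothing makes Section 3.4 override item 3, AEs are collected to last contact, and the safety population is not limited to randomised patients. A 7-month rule would also leave the events before folic acid unresolved.

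A reader might infer more than the documents support:

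- *A doubling of events.* That sets 12 months against 6, but Section 3.4 gives never-required patients 7 months, follow-up included.
- *A spurious deficit in recipients.* That requires counting recipients only from the start of folic acid and the others from enrolment. No section plans this.
- *Many extra AEs from denser visits.* Under Section 7.3.7, deteriorations in mandated laboratory values "should therefore only be reported as AEs if they fulfil any of the SAE criteria or are the reason for discontinuation of treatment", apart from associated symptoms. Questioning covers the whole time since the last contact (Section 7.3.6).
- *Observation that ends when olaparib stops.* Section 6.1.1 keeps such patients in visits and data collection.

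**Conclusion.** The concern holds as a minor one. The protocol conflicts on follow-up length and plans a crude AE comparison among undefined groups. For recipients against never-required patients, the ratio of event counts at equal rates is up to about 1.7 if 12 months from enrolment is followed, and 1.0 if the 7-month end binds. In the second case, 14% to 43% of recipients' time would still precede folic acid, for assumed starts at month 1 to 3. The 12/7 ratio uses protocol durations, read from enrolment and with complete observation; the AE rates and start months are assumptions. It would be wrong to infer that the randomised AE comparison is distorted by the visit schedule.

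**What to change.** Amend Section 8.4.2 and reconcile Section 1.1 item 3 with Section 3.4:

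1. Use one cut-off for all AE comparisons, 7 months from enrolment for every patient. List later events without comparing them.
2. Make randomised folic acid against placebo the main AE comparison, by assigned arm, counted from randomisation to that cut-off. Analysis by assigned arm matters because placebo patients can move to folic acid when Hgb falls below 10 g/dl.
3. Report recipients against never-required patients as descriptive only. Give patients with a first event per patient-month, or all events with an interval that allows for repeat events within a patient. A plain Poisson interval on total events would not allow for these. Assign time and events before folic acid to the unsupplemented state.

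The cost is protocol wording and a few table columns. AE dates (Section 7.3.4) and dosing records (Section 5.4) are already collected. There are three drawbacks. Events after month 7 are not compared. Patients randomised late contribute little time; one randomised at month 5 contributes 7 − 5 = 2 months. Item 3 also remains confounded, because recipients are selected for folate deficiency and anaemia and no denominator removes that.

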8.5 Interim analyses

We consider would be reasonable to initially accrue 30 patients and re-evaluate the need for continued accrual based on the percentage of patients who develop folate deficiency in this first phase.

8.5.1 Data monitoring committee (DMC)

A data monitoring committee will not be utilized for this study. The study will be monitored by the study investigators and information will be shared with the funder company (Astra/Zeneca).

Olaparib - ESR-18-13807

10. SUPPORTING DOCUMENTATION AND OPERATIONAL CONSIDERATIONS

Clinical Study Protocol - 6
Olaparib - ESR-18-13807

Appendix A Actions required in cases of increases in liver biochemistry and evaluation of Hy's Law

A 1 Introduction

This Appendix describes the process to be followed in order to identify and appropriately report cases of Hy's Law. It is not intended to be a comprehensive guide to the management of elevated liver biochemistries. Specific guidance on managing liver abnormalities can be found in Section 8.4 of the Clinical Study Protocol.

During the course of the study the Investigator will remain vigilant for increases in liver biochemistry. The Investigator is responsible for determining whether a patient meets potential Hy's Law (PHL) criteria at any point during the study.

The Investigator participates, together with AstraZeneca clinical project representatives, in review and assessment of cases meeting PHL criteria to agree whether Hy's Law (HL) criteria are met. HL criteria are met if there is no alternative explanation for the elevations in liver biochemistry other than drug induced liver injury (DILI) caused by the investigational medicinal product (IP).

The Investigator is responsible for recording data pertaining to PHL/HL cases and for reporting Adverse Events (AE) and Serious Adverse Events (SAE) according to the outcome of the review and assessment in line with standard safety reporting processes.

A 2 Definitions

Potential Hy's Law (PHL)

Aspartate aminotransferase (AST) or alanine aminotransferase (ALT) $\geq 3 \times$ upper limit of normal (ULN) **together with** total bilirubin (TBL) $\geq 2 \times$ ULN at any point during the study following the start of study medication irrespective of an increase in alkaline phosphatase (ALP).

Hy's Law (HL)

AST or ALT $\geq 3 \times$ ULN **with** TBL $\geq 2 \times$ ULN, where no other reason, other than the IMP, can be found to explain the combination of increases, e.g., elevated ALP indicating cholestasis, viral hepatitis, another drug.

For PHL and HL the elevation in transaminases must precede or be coincident with (i.e., on the same day) the elevation in TBL, but there is no specified time frame within which the elevations in transaminases and TBL must occur.

A 3 Identification of potential Hy's Law cases

In order to identify cases of PHL it is important to perform a comprehensive review of laboratory data for any patient who meets any of the following identification criteria in isolation or in combination:

- ALT $\geq 3 \times$ ULN

Clinical Study Protocol - 6
Olaparib - ESR-18-13807

- $AST \geq 3 \times ULN$
- $TBL \geq 2 \times ULN$

When a patient meets any of the identification criteria, in isolation or in combination, the central laboratory will immediately send an alert to the Investigator (and also to the AstraZeneca representative).

The Investigator will also remain vigilant for any local laboratory reports where the identification criteria are met, where this is the case the Investigator will:

- Notify the AstraZeneca representative
- Request a repeat of the test (new blood draw) by the central laboratory
- Complete the appropriate unscheduled laboratory CRF module(s) with the original local laboratory test result

When the identification criteria are met from central or local laboratory results the Investigator will without delay:

- Determine whether the patient meets PHL criteria (see Appendix A 2 for definition) by reviewing laboratory reports from all previous visits (including both central and local laboratory results)

The Investigator will without delay review each new laboratory report and if the identification criteria are met will:

- Notify the AstraZeneca representative
- Determine whether the patient meets PHL criteria (see Appendix A 2 for definition) by reviewing laboratory reports from all previous visits
- Promptly enter the laboratory data into the laboratory CRF

A 4 Follow-up

A 4.1 Potential Hy's Law criteria not met

If the patient does not meet PHL criteria the Investigator will:

- Inform the AstraZeneca representative that the patient has not met PHL criteria.
- Perform follow-up on subsequent laboratory results according to the guidance provided in the Clinical Study Protocol.

A 4.2 Potential Hy's Law criteria met

If the patient does meet PHL criteria the Investigator will:

Clinical Study Protocol - 6
Olaparib - ESR-18-13807

Determine whether PHL criteria were met at any study visit prior to starting Study treatment (See Section 8.4 Safety Reporting)

- Notify the AstraZeneca representative who will then inform the central Study Team

The Study Physician contacts the Investigator, to provide guidance, discuss and agree an approach for the study patients' follow-up and the continuous review of data. Subsequent to this contact the Investigator will:

- Monitor the patient until liver biochemistry parameters and appropriate clinical symptoms and signs return to normal or baseline levels, or as long as medically indicated
- Investigate the aetiology of the event and perform diagnostic investigations as discussed with the Study Physician.
- Complete the three Liver CRF Modules as information becomes available
- If at any time (in consultation with the Study Physician the PHL case meets serious criteria, report it as an SAE using standard reporting procedures.

A 5 Review and assessment of potential Hy's Law cases

The instructions in this section should be followed for all cases where PHL criteria are met.

No later than 3 weeks after the biochemistry abnormality was initially detected, the Study Physician contacts the Investigator in order to review available data and agree on whether there is an alternative explanation for meeting PHL criteria other than DILI caused by the IMP. The AstraZeneca Global Clinical Lead or equivalent and Global Safety Physician will also be involved in this review together with other patient matter experts as appropriate.

According to the outcome of the review and assessment, the Investigator will follow the instructions below.

If there is an agreed alternative explanation for the ALT or AST and TBL elevations, a determination of whether the alternative explanation is an AE will be made and subsequently whether the AE meets the criteria for a SAE:

- If the alternative explanation is **not** an AE, record the alternative explanation on the appropriate CRF
- If the alternative explanation is an AE/SAE, record the AE /SAE in the CRF accordingly and follow the AZ standard processes

If it is agreed that there is **no** explanation that would explain the ALT or AST and TBL elevations other than the IMP:

- Report an SAE (report term 'Hy's Law') according to AstraZeneca standard processes.

Clinical Study Protocol - 6
Olaparib - ESR-18-13807

- The ‘Medically Important’ serious criterion should be used if no other serious criteria apply
- As there is no alternative explanation for the HL case, a causality assessment of ‘related’ should be assigned.

If there is an unavoidable delay of over 3 weeks in obtaining the information necessary to assess whether or not the case meets the criteria for HL, then it is assumed that there is no alternative explanation until such time as an informed decision can be made:

- Report an SAE (report term ‘Potential Hy’s Law’) applying serious criteria and causality assessment as per above
- Continue follow-up and review according to agreed plan. Once the necessary supplementary information is obtained, repeat the review and assessment to determine whether HL criteria are met. Update the SAE report according to the outcome of the review amending the reported term if an alternative explanation for the liver biochemistry elevations is determined.

A 6 Actions required when potential Hy’s Law criteria are met before and after starting study treatment

This section is applicable to patients with liver metastases who meet PHL criteria on Study treatment having previously met PHL criteria at a study visit prior to starting Study treatment.

At the first on-study treatment occurrence of PHL criteria being met, the Investigator will determine if there has been a significant change in the patients’ condition[#] compared with the last visit where PHL criteria were met.[#]

- If there is no significant change, no action is required
- If there is a significant change, notify the AstraZeneca representative, who will inform the central Study Team, then follow the subsequent process described in Appendix A4.
- A ‘significant’ change in the patient’s condition refers to a clinically relevant change in any of the individual liver biochemistry parameters (ALT, AST or total bilirubin) in isolation or in combination, or a clinically relevant change in associated symptoms. The determination of whether there has been a significant change will be at the discretion of the Investigator; this may be in consultation with the Study Physician if there is any uncertainty.

A 7 Actions required for repeat episodes of potential Hy’s Law

This section is applicable when a patient meets PHL criteria on study treatment, and has already met PHL criteria at a previous on study treatment visit.

Clinical Study Protocol - 6
Olaparib - ESR-18-13807

The requirement to conduct follow-up, review, and assessment of a repeat occurrence(s) of PHL is based on the nature of the alternative cause identified for the previous occurrence.

The investigator should determine the cause for the previous occurrence of PHL criteria being met and answer the following question:

Was the alternative cause for the previous occurrence of PHL criteria being met found to be the disease under study (e.g., chronic or progressing malignant disease, severe infection or liver disease), or did the patient meet PHL criteria prior to starting study treatment and at first on-study treatment visit, as described in Appendix A 6

If **No**: Follow the process described in Appendix A 4.1.

If **Yes**: Determine if there has been a significant[#] change in the patient's condition compared with when PHL criteria were previously met.

If there is no significant change, no action is required.

If there is a significant change, follow the process described in Appendix A 4.

A 'significant' change in the patient's condition refers to a clinically relevant change in any of the individual liver biochemistry parameters (ALT, AST or total bilirubin) in isolation or in combination, or a clinically relevant change in associated symptoms. The determination of whether there has been a significant change will be at the discretion of the Investigator; this may be in consultation with the AstraZeneca Physician if there is any uncertainty.

Clinical Study Protocol - 6
Olaparib - ESR-18-13807

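### The 'No' branch of Appendix A 7 sends repeat potential Hy's Law cases to A 4.1 (criteria not met), which none of them can enter; the reference that fits is A 4.2

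*Combined protocol and SAP*

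**What the plan says.** Appendix A 2 defines PHL as AST or ALT at least 3 times the upper limit of normal together with total bilirubin at least 2 times that limit. A 4 then divides in two: A 4.1 for patients who do not meet PHL criteria and A 4.2 for patients who do. A 5 sets out the case review and states that it covers every case meeting the criteria.

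A 7 deals with repeat episodes. On scope it says "This section is applicable when a patient meets PHL criteria on study treatment", and it adds that the patient must already have met the criteria at an earlier on-treatment visit. The need for follow-up, review and assessment of the repeat "is based on the nature of the alternative cause identified for the previous occurrence".

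The investigator then answers a two-part question: was the earlier episode found to be due to the disease under study, "or did the patient meet PHL criteria prior to starting study treatment and at first on-study treatment visit" (the A 6 situation)? The answers lead to:

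- **No:** "Follow the process described in Appendix A 4.1".
- **Yes, nothing significant changed:** "If there is no significant change, no action is required".
- **Yes, significant change:** "If there is a significant change, follow the process described in Appendix A 4".

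A 6, for patients with liver metastases who met PHL criteria before and after starting treatment, says on a significant change to notify AstraZeneca's representative and "then follow the subsequent process described in Appendix A4".

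**The concern.** The 'No' branch names the one half of A 4 that excludes the patients being sent there. A 6 and the 'Yes' branch cite A 4 as a whole, so a PHL-positive patient reaches A 4.2 by its entry condition. Only the 'No' branch picks out a subsection, and it is the wrong one.

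The branch matters clinically. It holds repeat episodes where the underlying disease was not accepted as the earlier cause. By its wording it includes an earlier episode for which no alternative explanation was found, if the patient is still on treatment; A 5 has such an episode recorded as related to the study drug. At stake is the A 4.2 work-up: informing the central Study Team, monitoring to normal or baseline values, investigating the cause, and completing the liver CRF modules. An investigator who followed the reference literally could omit or delay these steps, or report a qualifying case as non-qualifying.

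**Working it through.** No arithmetic applies. The check sets the entry conditions side by side.

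1. **Who is in A 7.** PHL criteria met now, on treatment, and met at an earlier on-treatment visit.
2. **Who takes the 'No' branch.** Those for whom both parts of the question are answered no: the earlier episode was not due to the disease under study, and the A 6 pattern does not apply. All of them still meet PHL criteria now.
3. **Who may enter A 4.1.** Patients who do not meet PHL criteria. Steps 2 and 3 have no patient in common, so the number of A 7 patients who can satisfy the A 4.1 condition is 0.
4. **What A 4.1 orders.** Two actions: tell AstraZeneca's representative that the criteria were not met, and follow later laboratory results under the protocol. For an A 7 patient the first is a false statement.
5. **Who may enter A 4.2.** Patients who meet PHL criteria. Every A 7 patient does.
6. **Whether a lighter pathway could be intended.** A 7 does let handling depend on the earlier cause. Where it relaxes follow-up, it says so openly, and only when the disease or the A 6 pattern accounts for the earlier episode and nothing has changed. The 'No' branch is the opposite case. Even a deliberate reduction could not sensibly include a report that contradicts the section's own scope.

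Next, what A 4.2 contains and whether the documents ask for it elsewhere in this situation:

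| A 4.2 investigator action | Elsewhere for this branch |
|---|---|
| Check for PHL before treatment | Yes: A 3 look-back over all visits, and the A 7 question itself |
| Notify the representative, who informs the Study Team | In part: A 3 notifies the representative; the onward step to the Study Team is in A 4.2 |
| Monitor to normal or baseline | In part: section 7.3.3 for recorded AEs and SAEs; A 5 continues follow-up when the assessment is delayed |
| Investigate the cause | In part: A 5 must settle whether another explanation exists and speaks of obtaining the information needed, but does not expressly order tests |
| Complete three liver CRF modules | In part: A 3 requires laboratory CRF entry and A 5 requires the explanation or AE to be recorded; the three modules are named only in A 4.2 |
| Report as an SAE if serious | Yes: section 7.4.1 |

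The Study Physician contact described in A 4.2 also appears in A 5, no later than 3 weeks after the abnormality was first detected. If A 4.2 were skipped, most of its content would survive at least in part, but several specific steps would not be expressly ordered.

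**The case against.** The strongest reply is that the documents already lead to the right place. For each qualifying laboratory report, A 3 tells the investigator: "Determine whether the patient meets PHL criteria (see Appendix A 2 for definition) by reviewing laboratory reports from all previous visits". A 4.1 and A 4.2 each open with their own condition, so a reader sent to A 4.1 finds it false and the next subsection applies. A 5 covers every PHL-positive case by its own words. The note under Table 7 and section 7.3.8 send such patients to Appendix A as a whole. A false negative report is also unlikely to mislead for long: the investigator is in A 7 only because the criteria are met, and the central laboratory alert goes to AstraZeneca's representative as well. All of this stands. It limits the consequence, but it works only if the investigator notices that the specific instruction is wrong and overrides it.

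Three stronger readings are tempting, and the documents do not support them.

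- A reader might infer that these cases escape Hy's Law review altogether. They do not. The no-action exits in A 6 and A 7 do depart from A 5's full coverage, but none of them lies in the 'No' branch.
- A reader might infer that drug-induced liver injury is more plausible throughout this branch. It also holds earlier episodes explained by, for example, another drug (one of the alternatives listed in A 2), where the study drug had been discounted. The inference fits only part of the branch.
- A reader might infer that A 5 must be added to the 'No' branch. It already applies, and naming it there alone would suggest that it does not apply to the 'Yes' branch with significant change.

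**Conclusion.** The cross-reference is wrong as written, and A 4.2 is the reference that fits. The finding is a contradictory instruction in a liver-safety procedure, not a missing process. It rests on the current text of Appendix A alone and needs no outside figure.

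Its practical size is small. It requires two on-treatment PHL episodes in one patient, among 75 planned (section 8.2), with study end at 7 months from enrolment (section 3.4). That it should be uncommon is a judgement: the documents give no PHL rate, so the number of patients affected cannot be estimated. The consequence is a risk of missed or delayed work-up, not a certain one. No endpoint, sample size or planned analysis changes. It is a minor correction, but worth making because the error sits in an operative safety rule.

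**What to change.** In the 'No' branch of Appendix A 7, change the reference from A 4.1 to A 4.2. Nothing more is strictly needed. If the sponsor prefers to name A 5 as well, it should be named in both the 'No' branch and the 'Yes' branch with significant change, so that the two read consistently. The cost is one cross-reference in the next amendment (two small edits if A 5 is named), with no new visits, data or analyses.
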